Title: Minimization of Bleeding Related Adverse Drug Events in Plastic & Reconstructive Surgery

NCT03212365

Document date: 8.6.2020

Study Protocol

Patients

Eligible patients were 18 years of age or older, had a planned definitive plastic and reconstructive surgery operation under a general anesthetic, and had planned post-operative admission of at least two overnights. All patients had sequential compression devices placed in the OR and continued during inpatient admission. Patients were ineligible if they had any one of the following: contraindication to use of enoxaparin, intracranial bleeding or stroke, hematologic or bleeding disorder, known heparin-induced thrombocytopenia, creatinine clearance ≤ 30 mL/min, serum creatinine > 1.6 mg/dL, epidural anesthesia, or patient/surgeon desire to be provided with non-enoxaparin chemical prophylaxis after surgery. Patients who received peri-operative aspirin were eligible for the study. Patients whose gross weight was > 150 kg were excluded. There was no minimum study weight. All patients provided written informed consent prior to their planned definitive operation.

Study Procedures

Patients were randomized immediately after their planned definitive operation, following a direct conversation between the Principal Investigator ([name]), primary plastic surgeon, and consultant surgeons or physicians. Primary surgeons had the discretion to decline study participation based on intra-operative events, such as procedure less invasive than planned or concern for intra-operative bleeding. Eligible patients were randomized to enoxaparin 40mg twice daily or enoxaparin 0.5mg/kg twice daily.

Investigational Pharmacy randomized patients and then provided study drug in identical syringes containing clear liquid; all doses were diluted to 1.0cc volume. Patients received the

first dose of study drug as a subcutaneous injection between 7 and 8 hours after the procedure ended, and every 12 hours thereafter until discharge from the hospital.

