Statistical analyses were performed using Stata15 (StataCorp; College Station, Texas).

We compared patient-level variables (Tables 1 and 2) between groups using student's t-test for continuous variables, chi-square or Fisher's exact test for dichotomous variables, and Wilcoxon rank-sum test for ordinal variables.

The primary effectiveness outcome was avoidance of under-anticoagulation (peak aFXa <0.20 IU/mL). Initial sample size estimates for under-anticoagulation avoidance were obtained

from a prior clinical trial, which established that 90.4% of patients who received enoxaparin 40mg twice daily were not under-anticoagulated. We assumed the rate of not being under-anticoagulated was 90.4% in the weight-based group. The primary effectiveness analysis was a noninferiority analysis with a two-sided test at the 0.05 level. The noninferiority margin was set at -12%. To achieve 90% power using a two-sided comparison with alpha of 0.05, using a two-sided 95% confidence interval around the difference in proportions, 127 patients per group were needed. The noninferiority hypothesis was tested by a Poisson regression model for binary outcomes with robust standard errors. After the Poisson model was fit, marginal estimation was used to calculate the 95% confidence interval around the difference in proportions. This method took the two estimated proportions used in the risk ratio, subtracted them, and computed the confidence interval for non-inferiority testing. To obtain a two-sided noninferiority test p-value, we used a Wald post-test to compare the difference in proportions to the noninferiority margin constant -0.12.

The primary safety outcome was avoidance of over-anticoagulation (peak aFXa >0.40 IU/mL). Initial sample size estimates for over-anticoagulation were obtained from a prior clinical trial, which showed that 72.2% of patients who received enoxaparin 40mg twice daily were not over-anticoagulated. We assumed that weight-based dosing would increase the proportion of patients not over-anticoagulated to 90%. To detect this difference with 90% power using a two-sided comparison with alpha of 0.05, 100 patients per group were needed. For this outcome, a Poisson regression model for binary outcomes with robust standard errors was fitted.

The Data Safety and Monitoring Board reviewed unblinded 90-day VTE and bleeding data every six months. To avoid an increased risk for type I error, no interim analyses were performed on primary outcomes.

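### Neither primary model names a covariate, so baseline weight goes unused: a valid analysis that gives up a little precision, mainly on the safety outcome

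*Combined protocol and SAP*

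**What the plan says.** All references are to the combined protocol and SAP.

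- **Effectiveness model (Statistical Analysis).** "The noninferiority hypothesis was tested by a Poisson regression model for binary outcomes with robust standard errors". Then: "After the Poisson model was fit, marginal estimation was used to calculate the 95% confidence interval around the difference in proportions", and "This method took the two estimated proportions used in the risk ratio, subtracted them, and computed the confidence interval for non-inferiority testing". The margin is -12%.
- **Safety model (Statistical Analysis).** "For this outcome, a Poisson regression model for binary outcomes with robust standard errors was fitted". No subtraction step is described here.
- **Baseline variables (Statistical Analysis).** Their only stated use is descriptive: "We compared patient-level variables (Tables 1 and 2) between groups using" t-tests, chi-square or Fisher's exact tests, and rank-sum tests. None is carried into a primary model.
- **Weight (Patients; Study Procedures).** "Patients whose gross weight was > 150 kg were excluded", with no lower limit. "Eligible patients were randomized to enoxaparin 40mg twice daily or enoxaparin 0.5mg/kg twice daily". No stratification by weight is described.

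That weight is held for every patient is an inference from the exclusion rule and the weight-based dose, but a safe one. A methods publication is cited for outcome definitions and sample size. It is not part of these documents and may say more about the models.

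**The concern.** Both primary outcomes are cut-points of the peak aFXa reached on the initial dose. In the fixed arm that dose is 40/50 = 0.8 mg/kg at 50 kg, 40/80 = 0.5 at 80 kg and 40/150 = 0.27 at 150 kg. Lighter patients should therefore tend towards high levels and heavier patients towards low ones. The plan itself expects exposure per kg to matter: "We assumed that weight-based dosing would increase the proportion of patients not over-anticoagulated to 90"%, from 72.2%.

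A covariate that is recorded before treatment and tied by design to the outcome can tighten a marginal contrast without changing what is estimated. The plan already uses marginal estimation for effectiveness, so most of the machinery is in place. What is at stake is interval width, not validity.

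**Working it through.** **1. The plan's own figures reproduce without adjustment.**

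Effectiveness (90.4% in both arms, margin 0.12, one-sided 0.025, 90% power): n = (1.960 + 1.282)² × 2 × 0.904 × 0.096 / 0.12² = 126.6, so 127 per group, as stated. At 127 per group, SE = √(2 × 0.904 × 0.096/127) = 0.0370, the 95% half-width is 7.25 points and power is 90.1%.

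Safety (72.2% against 90%, two-sided 0.05, 90% power, usual two-proportion formula): 100 per group, as stated. At 127 per group power is about 96%. The planning risk ratio is 0.90/0.722 = 1.25. SE(log RR) = √[0.278/(127 × 0.722) + 0.10/(127 × 0.90)] = 0.0625, so the half-width is 0.123 on the log scale (interval 1.10-1.41).

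The sample size and the unadjusted analysis agree.

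**2. How strongly could weight predict? (assumption)**

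The documents give no weight distribution and no weight-aFXa correlation. One anchor comes from fitting a lognormal to the planning rates at 0.20 and 0.40 IU/mL:

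- Fixed arm (9.6% low, 27.8% high): log-SD = ln 2/(1.305 + 0.589) = 0.366.
- mg/kg arm (9.6% low, 10% high, both partly assumed by the plan): log-SD = ln 2/(1.305 + 1.282) = 0.268.
- 1 - (0.268/0.366)² = 0.46.

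If weight explains all of that narrowing, its R² for fixed-arm log-aFXa is 46%. I take 10-46% as the range.

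**3. Large-sample variance ratio, adjusted to unadjusted.**

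Let p(z) = Φ[(a + √R² z)/√(1 - R²)] be the fixed-arm probability at standardised log weight z, with a = Φ⁻¹(P_f), and let V be its variance. With no weight effect in the mg/kg arm:

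- Risk difference: 1 - (V/2)/[P_f(1 - P_f) + P_w(1 - P_w)]
- Log risk ratio: 1 - (V/2P_f²)/[(1 - P_f)/P_f + (1 - P_w)/P_w]

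At R² = 46%, noninferiority: V = 0.0191, so 1 - 0.0095/0.1736 = 0.945. Safety log ratio: V = 0.0573, so 1 - 0.0549/0.4962 = 0.889.

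**4. The planned Poisson family at 127 per arm.**

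These are simulated figures: 40,000 trials per setting, arm-by-weight interaction, standardised over all patients, influence-function SE. Half-widths are the unadjusted value times the square root of the Poisson ratio.

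| R² | NI, limit | NI, Poisson | NI half-width (points) | Safety log RR, limit | Safety log RR, Poisson | Safety half-width (log) |
|---|---|---|---|---|---|---|
| none used | 1 | 1 | 7.25 | 1 | 1 | 0.123 |
| 10% | 0.991 | 0.995 | 7.23 | 0.978 | 0.981 | 0.121 |
| 20% | 0.980 | 0.987 | 7.20 | 0.955 | 0.965 | 0.120 |
| 46% | 0.945 | 0.965 | 7.12 | 0.889 | 0.916 | 0.117 |

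Repeat runs with fewer trials at 46% gave 0.965-0.972 (noninferiority) and 0.916-0.928 (safety). At 46% the planning safety interval moves from 1.10-1.41 to 1.11-1.40. A logistic working model comes closer to the limit (0.948 and 0.888 at 46%).

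**5. Power, error rate and downside.**

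- Noninferiority power changes by -0.2 to +0.3 points with no weight effect in the mg/kg arm.
- At a true difference of -12%, false noninferiority is 2.7-3.0% adjusted against 2.8-3.0% unadjusted. Coverage is 94.5-95.2%.
- If weight predicts nothing, variance rises by about 0.2-0.5%.
- If weight explains 10% in the mg/kg arm in the opposite direction, the noninferiority ratio is 1.000-1.005, power falls 0.3-0.7 points, and the safety log-ratio is 0.955-0.996.
- If it acts in the same direction, the ratios are 0.926-0.975 and 0.875-0.962.

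**The case against.** The strongest reply is that nothing is wrong. Leaving a randomised comparison unadjusted is a legitimate choice, 127 and 100 per group follow from it, and the outcome that sets the sample size gains essentially no power. The size of the gain rests on an assumed R², and the text is in the past tense, so the primary analysis may be closed. All of that stands, and it limits the point to an optional improvement. It does not remove it: the data are already held, the contrast and margin stay the same, and the cost is close to nil.

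A reader might infer more than the documents support:

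- **That the unadjusted result is biased or exposed to weight imbalance.** Randomisation protects it, and its standard error already covers chance imbalance.
- **That patients could have been saved.** Shrinking the variance by the full log-aFXa R² would be wrong: the outcome is dichotomised and weight may matter in one arm only. Even scaling by the 0.965 ratio suggests about 91.1% power (0.12/0.0370/√0.965 - 1.96 = 1.34), and the simulations do not bear that out. Safety needs only 100 per group against 127.
- **That R² could be well above 46%.** At 55% the fixed-arm residual log-SD would be 0.366 × √0.45 = 0.246, below the 0.268 implied for the mg/kg arm.
- **That the safety contrast is undefined.** The effectiveness text describes the proportions as those entering the risk ratio and treats subtraction as an extra step. A Poisson model without that step points to a risk ratio.

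**Conclusion.** The point holds as a modest, low-cost improvement, not an error. As written, both primary models read as unadjusted, valid and adequately powered. Using baseline weight would bring a very small gain for noninferiority and a somewhat larger one for the safety risk ratio, at the sizes tabulated above. No conclusion on noninferiority is likely to turn on it.

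The sizes depend on three things that the documents do not give: the fixed-arm R² (10-46% assumed, the top anchored partly to the plan's own assumed mg/kg rates), the absence of a weight effect in the mg/kg arm, and a lognormal aFXa. With opposing slopes the noninferiority gain is nil; with no prediction there is a trivial loss. The cited methods publication could also show that adjustment was already considered.

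**What to change.** **If the analysis can still be prespecified:**

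- Add log(baseline weight) and its interaction with arm to each primary Poisson model. A logistic working model is slightly more efficient and may be used instead.
- Standardise over the baseline weights of all patients analysed for that outcome, with unconditional robust standard errors.
- For effectiveness, report the same marginal risk difference against -12% with the same Wald test. For safety, report the same marginal risk ratio.
- Keep the unadjusted result as supportive.
- Use baseline weight, not mg/kg received, which depends on the assigned arm.

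**If the primary analysis is locked or done**, leave it unchanged and report the weight-standardised result as one labelled sensitivity analysis per primary outcome. Promoting it to primary once results are known would be post hoc.

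**Cost:** no new data, and two extra terms per model. The effectiveness analysis already has its marginal step; the safety analysis would need one. The statistical price in the unfavourable cases is under 1 point of noninferiority power.
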